#### **3.5.2 Electrode arrays**

The surgeon may elect to use one of two types of lateral-wall electrode arrays that are available for the Neuro Zti. The two electrode arrays are the Neuro ZtiCLA and the Neuro ZtiEVO. Both arrays have been extensively used OUS for several years on the prior generation implant and now in OUS implantations of the Neuro Zti. Both arrays provide 20 contacts, similar cochlear coverage and are amenable to round-window, modified round-window or cochleostomy insertions into the scala-tympani. To date, there is no evidence that speech perception outcome is impacted by the array choice and both of the array's dimensions are much smaller than the scala-tympani dimensions reported in the literature. Both arrays demonstrate stiffness profiles that fall within those demonstrated in existing designs by other manufacturers currently approved by the FDA. At present, the choice is left to the surgeon's preference. The principle difference between the arrays are that the "Classic" Array is slightly stiffer than the "EVO" making it slightly easier to achieve a full insertion. However, the less stiff EVO, is suspected to allow for a "softer" insertion which under certain conditions may result in a lower probability of cochlear trauma. To date, the EVO version is the most common electrode array used and the classic version tends to be used in cases of more difficult insertion due to anatomical issues or other issues that result in difficult insertion such as compromised patency of the scala-tympani due to fibrosis or ossification. Temporal bones studies have been conducted for both arrays and this data will also be provided in the PMA application.

#### **3.5.3 Study Treatment or Diagnostic Product Procedures**

Subjects are to be candidates for a cochlear implantation as assessed by tests and exams performed before surgery and are of clinical routine evaluation/use. The conventional surgical approach is described below. If an alternative surgical method or approach is used (e.g. suprameatal, cranial facial, or endomeatal approach), the subject should be excluded from the protocol and the investigator shall record this information in the CRF and document the rationale for the deviation in surgical approach.

---

 Tympanometry can be performed within 6 months before the visit 2 (inclusion visit).

The standard mastoidectomy-posterior tympanotomy introduced by House, 1961, is the gold standard for cochlear implantation, however some surgeons modified their approach to develop simplified and safer procedures, which is adaptable to possible situations such as anatomical anomalies or to have a shorter operative time and minimal morbidity with a possible decrease of facial nerve damage and chorda tympani sacrifice.

The Neuro CIS does not require special surgical techniques when compared to the CISs currently approved by the FDA and in Europe. The exception being that the Neuro Zti incorporates an integrated fixation system to prevent device migration.

The approach uses the facial recess is the well-known technique and used for many decades, other surgical technique used in this clinical trial will exclude the subject.

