### 3.6.2 Outcome Data and Data Analysis

#### 3.6.2.1 Analysis Set

##### a) Full Analysis Set (FAS)

This set will include all subjects implanted with the device, regardless whether any post-operative data are available. The primary analysis will be performed on a subgroup of this set. This subgroup is composed of English speaking patients to avoid the probable effect of language on the response.

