##### b) Per-Protocol Set (PPS)

This set of patients is composed of participants who complete the clinical trial according to the protocol.

It consists of subjects who satisfy the following criteria:

- Complete the pivotal study
- Protocol compliance during the pivotal study (complete post-implantation visits)
- No violation of any eligibility criteria that could influence the primary efficacy endpoint
- No violation of the protocol or deviation from the protocol which could influence the outcome of efficacy endpoints.

The type of protocol violation and protocol deviations that are considered to influence the outcome of the safety endpoints will be defined in the statistical analysis plan.

The English speaking subgroup in the PPS will be used in a sensitivity analysis of the primary analysis.

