### **c) Safety Analysis Set (SAS)**

It consists of all subjects for whom surgery for implantation started.

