### 1.2.1.2 *Electrodes*

The Neuro Zti may be configured with either the “Classic” or “EVO” array; these two product configurations are designated as Neuro ZtiCLA and Neuro ZtiEVO, respectively. A schematic of the two electrode options can be seen in Figure 3, while detailed information regarding the arrays is further outlined in Section 1.5. The arrays are both constructed from the same raw materials with the contacts being machined from platinum/Iridium (10%). The wires between contacts and the receiver/stimulator are coated with PTFE for electrical isolation. The PTFE coated wires are completely embedded inside an over-molding comprised of medical grade silicone; therefore, the wires are not in contact with the tissues.

The principal differences between the two electrode array options are that the Neuro ZtiEVO has a slightly smaller form factor allowing for reduced stiffness and may be more suitable for “softer” surgery. Both arrays are currently approved for use in Canada and the European Union and have been used with the prior generation device, Digisonic SP. The company makes no specific warranty or prescription as to which array is most appropriate for a given patient; thus leaving the array choice to the preference of the surgeon. Furthermore, there are no specific restrictions as to the surgical approach to the cochlea (ie. traditional mastoidectomy vs transtympanic approach) or to the introduction of the array into the cochlea (round window vs cochleostomy approach). Both arrays may be inserted (and re-inserted if necessary) into the scala-tympani using the same techniques.

**Figure 3:** Schematic showing the EVO and CLASSIC electrode array options for the Neuro Zti

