### 4.3. Safety Analysis Set (SAS)

The Safety Analysis Set will include all patients for whom the surgery of implantation started.

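### Subjects operated by another approach are excluded from the protocol at surgery but stay in the full and safety sets, with no rule for their follow-up in the co-primary safety rate

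*Protocol*

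**What the plan says.** Protocol 3.5.3 states the exclusion twice. If an alternative approach is used, "the subject should be excluded from the protocol and the investigator shall record this information in the CRF", together with the reason for the deviation. The section closes by saying that any "other surgical technique used in this clinical trial will exclude the subject".

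The analysis sets make no exception for these subjects:

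- **Full analysis set** (Protocol 3.6.2.1 a; SAP 4.1 agrees): "This set will include all subjects implanted with the device, regardless whether any post-operative data are available".
- **Safety set**, Protocol 3.6.2.1 c: "It consists of all subjects for whom surgery for implantation started". SAP 4.3 agrees: "The Safety Analysis Set will include all patients for whom the surgery of implantation started".
- **Per-protocol set** (Protocol 3.6.2.1 b; SAP 4.2 agrees). This is the only set with a criterion that could remove them: "No violation of the protocol or deviation from the protocol which could influence the outcome of efficacy endpoints".

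The co-primary safety result is the major-complication rate over the first year, given as a proportion with an exact 95% interval and no formal test (Protocol 3.6.1.1 b and 3.6.2.3; SAP 6.2). SAP Table 9.1 has rows for Yes, No and the interval only.

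**The concern.** The trigger is the approach actually used, so it takes effect at or after visit 3, when the subject has already been consented, included and operated on. From then on the subject belongs to both the full and the safety sets. Neither document says whether exclusion from the protocol means the end of study visits, removal from an analysis set, or both.

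If it means the end of visits, two results are exposed.

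- **Safety.** The co-primary proportion assumes that each subject's status over the first year is known. A subject seen for only a few weeks could stay in the denominator with no event on record. The early safety trigger in Protocol 3.6.4 and 3.6.5 also counts recorded major complications, so an unseen event would be missing there too.
- **Efficacy.** An English-speaking subject in this position would have no observed month 6 score, and the primary analysis would rest on imputation or a missing value.

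This would be avoidable loss of follow-up, caused by a protocol rule and tied to something that happens after enrolment.

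**Working it through.** **1. The plan's own safety figures (Protocol 3.6.1.4).** At a 2% rate with 50 subjects, the chance of at least one event is 1 − 0.98^50 = 63.58%; the plan gives 63.5%. The exact (Clopper-Pearson) upper limit for 1/50 is 10.65%; the plan gives 10.6%. Both reproduce, so no stated number is in dispute.

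**2. What would be recorded after exclusion.**

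| Provision | Effect |
|---|---|
| Protocol 3.5.7, visit 3 | Complications at surgery are recorded |
| Protocol 3.5.4 | A withdrawn subject has an early-termination assessment, is then followed as any implanted patient, and efforts are made to document outcome; continued study visits are not promised |
| Protocol 4.5.2 | Adverse events go on the CRF until 28 days after the subject's final visit; a later serious event must be reported only if the device is suspected as the cause |
| Protocol 3.5.5.2 | Major complications count whether or not they are related to the device |
| SAP 5.6.2 | Complications are limited to those related to the surgery or the device |

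Under Protocol 3.5.5.2 a late qualifying event could therefore stay out of the database. The narrower SAP definition shrinks the gap but does not close it, because the adverse event form rates relation to the device and relation to the procedure separately.

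**3. Size for the safety rate.** The number of such subjects, k, is not in the documents. I assume k = 1 to 5. Suppose one major complication is recorded elsewhere in the trial; exact 95% intervals are in brackets.

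| Scenario | N = 50 | N = 55 |
|---|---|---|
| All k counted without an event | 1/50 = 2.0% (0.1 to 10.6) | 1/55 = 1.8% (0.0 to 9.7) |
| One of the k had an unseen event | 2/50 = 4.0% (0.5 to 13.7) | 2/55 = 3.6% (0.4 to 12.5) |
| All of k = 3 had unseen events | 4/50 = 8.0% (2.2 to 19.2) | 4/55 = 7.3% (2.0 to 17.6) |
| All of k = 5 had unseen events | 6/50 = 12.0% (4.5 to 24.3) | 6/55 = 10.9% (4.1 to 22.2) |

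SAP section 3 leaves missing data out of percentage denominators by default. Doing that here would conflict with the safety set definition but barely move the rate: at N = 50 it is 1/49 = 2.0% for k = 1 and 1/45 = 2.2% for k = 5. The exposure comes from unseen events, not from the denominator.

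The last two rows are extremes. If these subjects carried the protocol's own rates (2% from 3.6.1.4 or 7.1% from 3.6.4) and every event were missed, the expected understatement on 55 subjects would run from 1 × 2% / 55 = 0.04 points to 5 × 7.1% / 55 = 0.65 points.

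**4. Size for efficacy.** None of the six imputation rules (Protocol 3.6.3.1; SAP section 3) names this case. The closest is Rule 5, which sets month 6 equal to baseline, a change of zero. Take 39 English speakers, k of them at zero and the rest at the planning values of 50 ± 25:

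- mean m = 50 × (39 − k) / 39
- variance = [(38 − k) × 25² + (39 − k)(50 − m)² + k m²] / 38
- k = 1: m = 48.7, SD 25.9, t = 11.7, lower 95% limit 40.3
- k = 5: m = 43.6, SD 28.8, t = 9.5, lower 95% limit 34.3

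Each such subject costs about 50/39 = 1.3 points. The test against zero is not threatened.

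**The case against.** The best defence is that the remedy is already one natural reading. Section 3.5.3 itself treats another approach as a deviation to be recorded with its reason, the per-protocol criteria can remove deviations, and the other two sets are untouched. Section 3.5.4 adds an early-termination assessment and continued care as an implanted patient. A planned change of approach might also be spotted before surgery. The Kaplan-Meier analysis in Protocol 3.6.2.4 g and SAP 6.4 can censor short follow-up. This shows that the risk is reduced. It does not remove the stated rule that the subject is excluded, and the Kaplan-Meier analysis covers the first minor or major complication, not the co-primary rate.

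Four stronger readings are tempting and are not supported.

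- **That these are the hardest operations.** Section 3.5.3 says that "some surgeons modified their approach to develop simplified and safer procedures", and gives shorter operating time and low morbidity as reasons beside anatomical anomalies. Inclusion criterion 7 and preoperative imaging already screen for anatomical obstacles. The direction of any link between approach and risk is not established.
- **That the plan prescribes counting them as event-free.** No text says so; it is a possible consequence of truncated recording.
- **That imputation would favour the device.** Rule 5 would work against it. Rule 4 could impute a predicted gain, but it is written for loss to follow-up or consent withdrawal for unknown reasons.
- **That Appendix 1 contradicts the exclusion.** Section 1.2.1.2 says "there are no specific restrictions as to the surgical approach to the cochlea", but it describes what the product permits, and a trial may specify a narrower technique. The tension is weak.

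**Conclusion.** The point holds as a conflict between the exclusion rule and the analysis sets, with a gap in the handling of incomplete follow-up. Followed as written, section 3.5.3 can end study observation for operated subjects whom the full and safety sets retain, and the co-primary proportion has no rule for them.

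The likely effect is small. One missed major complication would halve the reported rate in the 2/55 against 1/55 illustration, but that requires an excluded subject who has a major complication which then goes unrecorded. The size rests on an assumed one to five such subjects. No formal safety test depends on the result, and the efficacy conclusion would not change under the planning assumptions. It is worth correcting because the loss of data is avoidable and the co-primary safety estimate rests on only 50 to 55 patients.

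**What to change.** Reconcile Protocol 3.5.3 with 3.5.4, 3.6.2.1 and 3.6.3.1, and carry the result into the SAP:

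1. State that a different surgical approach is a recorded protocol deviation that removes the subject from the per-protocol set only.
2. State that these subjects keep their scheduled HINT and safety visits to month 12, so that the full and safety sets hold observed data.
3. In SAP 6.2, say how subjects with incomplete 12-month follow-up enter the major-complication rate. A Kaplan-Meier 12-month estimate beside the proportion, and a sensitivity analysis counting such subjects as events, would be enough.

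The cost is a few sentences, one small extra analysis and ordinary follow-up of a few patients. The change concerns follow-up and analysis sets only; it takes no view on which surgical approach should be used.

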### **Surgical Procedure**

The surgeon performing CI surgery, in this study, shall be experienced in otologic and neurotologic surgery. The surgeon shall also be experienced in cochlear implantation. The CI surgery is to be done under general anesthesia with a minimally invasive technique. The classical/conventional technique for cochlear implantation is to be performed for this study:

- A small postauricular incision shall be made and the temporal muscle and periosteum shall be elevated,
- The bone shall be exposed anteriorly to the level of the ear canal and posteriorly sufficient to accommodate the Neuro Zti's electronic housing.
- Mastoidectomy and posterior tympanotomy are to be performed with an extended facial recess approach.
- The tympanic membrane and the ear canal are not to be disturbed during the surgical procedure.
- For a round window (RW) insertion of the electrode, the posterior tympanotomy recess shall be drilled sufficiently to obtain a clear view of the round window (RW) and to obtain proper landmark identification to ensure electrode insertion into the scala-tympani. If warranted, the round-window niche should be reduced to expose the round window.
- A cochleostomy approach may also be considered, however, proper landmark identification and insertion vector shall be determined as standard for FDA approved CI systems to ensure scala tympani insertion.
- Prior to opening the cochlea, either the RW membrane for RW insertion or the endosteum for the cochleostomy, a drop of corticosteroid and/or hyaluronic acid may be placed on the RW membrane or endosteum to reduce fibrotic reaction.
- Once scala-tympani access to the cochlea is verified, the Neuro Zti shall then be placed in its position under the periosteum, posterior and superior to the ear and secured with the included self-tapping screws. Device positioning may be helped by use of included sterile surgical dummies of internal and external components.
- The RW membrane or endosteum shall then be incised and the tip of the electrode array shall be guided toward the cochlear opening. During insertion, no excessive force should be used (biocompatible lubricants may help smooth insertion).

- Following electrode insertion, the cochlea shall be sealed with a piece of fascia graft and/or bone wax, bone paté. The periosteum shall be sutured over the implant region and the mastoid cavity.
- The wound shall then be closed in layers with subcutaneous sutures and a suitable dressing shall be applied.
- For each implantation the surgeon shall be required to document the duration of the surgery (starting time i.e. skin incision, and ending time i.e. last skin flap suture).

After surgery, the rehabilitation procedures for study subjects shall be managed similar to FDA approved CI recipients (i.e. sound processor activation/fittings/mappings, speech therapy).

### **3.5.3.1 Allocation to Treatment**

Not applicable.

Open label-trial.

A single identification number (SSID) is assigned at the inclusion visit that uniquely identifies each subject, it is composed of the site code and subject number |\_|\_|-|\_|\_|. The same CI system models shall be assigned for all subjects. The sound processor is available in different colors but the hardware and electronic features are identical between processors.

### **3.5.3.2 Breaking the Blind**

Not Applicable

### **3.5.3.3 Treatment Adherence/Study Compliance**

The importance of rehabilitation and study visit attendance shall be discussed with each subject.

The cochlear implant system must be used for at least 8 hours per day; system use will be verified via the subject diary. If a subject fails to utilize their cochlear implant system for at least 8 hours per day for more than 10 consecutive days and/or less than 85% of the total required wearing time for the study, the audiologist will ask the subject about the issue(s) and suggest alternatives.

This survey will provide useful information on subject complaints.

### **3.5.4 Withdrawal of Subjects Due to Non-Compliance**

Subjects who are not compliant with study visits shall be withdrawn from the study. Subjects may withdraw from the trial at any time at their own request, or they may be withdrawn at any time at the discretion of the PI and/or the sponsor for safety, behavioral, psychological or administrative reasons. If the subject does not return for a scheduled visit, every effort shall be made to contact the subject. Regardless, every effort will be made to document subject outcome for all participants in the study.

For each subject that withdraws from the assessments detailed in the schedule of activities for visits, an “Early termination” shall be carried out. If the subject withdraws from the trial and also withdraws consent for disclosure of future information, no further evaluations will be performed and no additional data will be collected. The sponsor may retain and continue to use any data collected prior to the withdrawal of consent. Any withdrawn subject will be followed as a CI implanted patient and followed per regulatory guidelines.

Withdrawn subjects will not be replaced unless the total number of remaining subjects drops below 50 (10% loss). Should a subject withdraw or be withdrawn due to non-compliance, all available data regarding those that withdraw or are withdrawn will be provided and documented as a subgroup in a due-diligence effort to determine if a failure of the device to perform to specification was the reason or contributed to the reason of withdrawal or non-compliance.

The subject cannot participate in another study during this study. However, as there is no wash-out period at the end of this study, the subject can participate in another clinical trial at the end of this study.

### **3.5.5 Follow-up Procedures**

An Oticon Medical Clinical Support could support the medical team in fittings and objective measurements. Roles and tasks are described in Appendix 6, the clinical support provides an assistance to the clinical team and should not interfere with subject clinical results.

#### **3.5.5.1 Procedures to Assess Efficacy**

For the timing assessments please refer to the schedule of activities in section 3.5.5.4.

Audiometric testing shall be performed by or under the direct supervision of an otolaryngologist, a qualified hearing aid acoustician/specialist, speech-pathologist, technician and/or by an audiologist qualified to perform such tests. The pivotal study should not disrupt the routine follow-up visits of each referral center (i.e. fittings, programming changes, speech therapy, audiology tests, and radiological control).

All subjects will use the same signal processing (e.g. directional microphone) and stimulation strategy (e.g. pulse shape, pulse rate).

All subjects, English and non-English speakers, will be assessed with the same procedure and setups

The Danish (20-sentences-list), the French Canadian (20-sentences-list) and the American English HINT (20-sentences-list) will be used according the local language.

The HINT tests will be conducted with dedicated HINT software.

##### **a. Description**

The HINT (Hearing in noise Test) was developed at the House Ear Institute (Los Angeles, California) and measures speech recognition thresholds in quiet and noise [3]. When used to determine implant candidacy, the HINT sentences are generally presented in quiet.

The HINT is recognized as a primary assessment instrument for measuring a subject's ability to hear in quiet and in noise. HINT was originally designed as an adaptive speech recognition test based on a correct response of the entire sentence [3]. An intensity level measurement for the sentence speech-reception threshold was determined by presenting random HINT sentences in competing speech-shaped noise (SSN). However, current clinical use of HINT sentences routinely deviates from this original design; instead, HINT sentences are presented in quiet to obtain an accuracy measure, which is important for determining cochlear implant candidacy [4]. Disability evaluation under social security, requires that this testing be conducted in quiet at 60dB SPL [10].

A digital recording is presented to the subject placed inside a sound isolation booth.

For this protocol, subjects shall be tested with two sentence lists

- during inclusion (visit 2)
  - in quiet and in noise in the best aided condition and
- at 3, 6 and 12 months (visits 6, 7 and 8 respectively)
  - in quiet and
  - in noise condition in the ipsilateral electrically stimulated ear with an occluded contralateral ear.

The noise and/or the signal shall be presented from the front of the recipient at 0° azimuth

